For qualitative interview data, transcribed interviews will be coded by study team members using an iterative process that begins with open coding, codebook development and refinement, and consensus regarding the codes. We will use an integrated approach, with a priori codes based on prior work and themes emerging from the data. Once a stable codebook is developed, approximately 20% of the data will be double coded for reliability purposes (weighted kappa). Separate codebooks may be developed for the Sleep Well! participant interviews and for the enhanced usual care condition interviews. We will also explore how themes from the intervention group vary by quantitative caregiver-reported outcome data (e.g., sleep problem perception) and family factors (e.g., shiftwork). We will also examine variation using this method for the usual care group interviews.

Data analysis for the secondary sleep outcomes (below) will include (1) the application of mixed effects growth models, and (2) generating effect sizes, as follows.

- (1) Mixed effects linear growth models will also be applied to compare overall change in continuous outcomes between groups from pre-intervention to follow-up using an intent to treat approach with maximum likelihood estimation. Individual variability in the outcomes from pre-intervention through the follow-up assessments will be predicted by a two-level fixed effect condition variable (coded 0 for enhanced usual

care and 1 for intervention), a time variable with the intercept defined as the pre-intervention assessment and weeks between this assessment and last follow-up, and the group  $\times$  time interaction. Models will account for random effects (intercept, time) and fixed effects (group, and time by group). The time by intervention group interaction identifies whether there is a significant between-group difference in change since pre-intervention. Categorical outcomes will be modeled as mixed-effects growth models with maximum likelihood and a logit link. Model parameters include those described for the continuous models and a threshold parameter at each timepoint. Any sleep and behavior outcomes that are significantly different by group at pre-intervention will be included as covariates in all models.

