- (2) Effect sizes for the magnitude of group differences will be drawn from the mixed effects models. The effect size for the condition  $\times$  time interaction is equivalent to Cohen's d-statistic. For categorical outcomes, percent change in the odds for the condition  $\times$  time interactions are provided as a measure of effect size.

Secondary sleep outcomes for these analyses will be drawn from the caregiver-rated Brief Child Sleep Questionnaire (BCSQ) and actigraphy (objective sleep measurement) and will include:

- Child sleep problems (BCSQ)
- Child bedtime resistance (also called "bedtime difficulties" BCSQ)
- Child sleep onset latency (BCSQ)
- Child night awakenings (frequency and duration BCSQ)
- Child sleep quality (BCSQ)
- Child total (BCSQ) and nighttime sleep duration (BCSQ and sleep onset to offset for actigraphy)

To examine secondary child behavior outcomes, we will examine change by group over time from pre-intervention to follow-up, exactly as described for the sleep outcomes (see above).

Secondary behavior outcomes drawn from validated the following validated clinical measures include:

- Child externalizing problems composite T-score (Child Behavioral Checklist for ages 1.5-5 years)
- Child internalizing problems composite T-score (Child Behavioral Checklist for ages 1.5-5 years)

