## 6.5 Sample Size and Power

As is appropriate for a pilot study, the primary goal of this study to estimate effect sizes to fully power a future large-scale randomized controlled trial of the adapted behavioral sleep intervention through a subsequent R01 submission. However, we will have adequate power to detect the expected medium effects (found in similar efficacy and effectiveness trials for sleep) between groups on sleep outcomes. Based on previous primary care behavioral intervention research studies conducted at CHOP, we expect an approximate attrition rate of 15% at follow-up. A final sample size of 68 participants yields  $>80\%$  power to detect medium (0.5 SD) between-group effects using linear regression and adjusting for covariates (pre-intervention scores; socio-demographic variables) to evaluate change in sleep outcomes. The proposed sample of 80 dyads is thus sufficient for detecting medium intervention effects and accounts for potential attrition. Medium effects for relevant child sleep outcomes are equivalent to a  $\sim$ 10-minute reduction in sleep onset latency, a 30 to 40-minute increase in sleep duration, and a reduction of  $\sim$ 1 night awakening—all clinically meaningful results.

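### The significance-triggered baseline covariate in 6.4, entered as a main effect, does not on average correct the tested group-by-time effect, and the power in 6.5 belongs to a different analysis

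*Combined protocol and SAP*

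**What the plan says.** Section 6.4 fits mixed linear growth models from pre-intervention to follow-up, "using an intent to treat approach with maximum likelihood estimation". The time variable starts at the pre-intervention assessment, so the baseline score is the first response. The terms are listed as follows: "Models will account for random effects (intercept, time) and fixed effects (group, and time by group"). The test is the interaction: "The time by intervention group interaction identifies whether there is a significant between-group difference in change since pre-intervention".

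Baseline scores otherwise enter only through a significance rule: "Any sleep and behavior outcomes that are significantly different by group at pre-intervention will be included as covariates in all models". No interaction of that covariate with time is mentioned. For moderators, under the additional exploratory analyses, 6.4 does write out the interactions with condition and time.

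On effect sizes, 6.4 says: "Effect sizes for the magnitude of group differences will be drawn from the mixed effects models". Section 6.5 describes "the primary goal of this study to estimate effect sizes to fully power a future large-scale randomized controlled trial".

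Section 6.5 claims more than 80% power at a final N of 68 for 0.5 SD "between-group effects using linear regression and adjusting for covariates (pre-intervention scores; socio-demographic variables) to evaluate change in sleep outcomes". On losses it says "we expect an approximate attrition rate of 15% at follow-up", which is why 80 dyads are proposed.

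**The concern.** Two separate things do not fit.

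First, the rule is meant to deal with chance baseline imbalance, but the tested quantity is a change from a baseline that is itself a response. If one arm starts higher by chance, regression to the mean pulls its change down relative to the other arm. A covariate that shifts a child's whole line up or down by the same amount at every visit does not alter the difference in slopes. A report could call an effect size adjusted for baseline although the adjustment had, on average, removed none of the shift, and that effect size is intended for planning the next trial.

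Second, the power statement describes a regression that always conditions on baseline and socio-demographic variables. The fixed effects listed in 6.4 contain neither, so the figure cannot be read as the power of the planned test.

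**Working it through.** **Inputs from the documents.** N=68 analysed, 80 randomised, 15% attrition and 0.5 SD (6.5); post-intervention at weeks 9-16 and follow-up at weeks 15-24 (3.1.4).

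**Assumed, because not stated.** 1:1 allocation, two-sided 0.05 for both the trigger and the tests, visits at weeks 0/12/20, SD=1, and equal correlation rho between visits. Rho is shown at 0.3/0.5/0.7.

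**The plan's own figures.** 68/(1 - 0.15) = 80 reproduces. Unadjusted power for 0.5 SD at 34 per arm is 53%. With adjustment, two-sided power above 80% needs the covariates to explain about 47% of the variance; one-sided, about 33%. Neither value is given. A regression F test with f² = 0.15 and two tested predictors does give 80.4% at N=68, but 0.5 SD corresponds to f² = 0.0625. Section 6.5 does not say that this route was used.

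**Part (a): the shift.** Mean visit week is 10.67 and Sxx = 202.67. The 20-week slope contrast has weights -1.053, 0.132 and 0.921. With no treatment effect and a baseline imbalance D, the expected later differences are rho × D. The contrast is then

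-1.053 D + (0.132 + 0.921) rho D = -1.053 (1 - rho) D,

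that is, -0.74/-0.53/-0.32 of D. At 40 per arm a just-significant imbalance is 1.99 × √(2/40) = 0.445 SD, so at rho 0.5 the shift is about -0.23 SD.

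**Part (a): what the covariate does.** Maximum likelihood fits with random intercept and slope, 1,050 null trials per rho in which the rule fired, 40 per arm:

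| | rho 0.3 | rho 0.5 | rho 0.7 |
|---|---|---|---|
| Mean shift, complete data, without or with covariate (SD) | -0.38 | -0.28 | -0.16 |
| Mean shift, 15% attrition, without / with (SD) | -0.39 / -0.40 | -0.29 / -0.29 | -0.17 / -0.17 |
| Mean SE, complete data, without / with | 0.264 / 0.285 | 0.223 / 0.244 | 0.174 / 0.192 |
| Type I error in these trials, complete data, without / with | 24 / 17% | 20 / 15% | 12 / 7% |

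With complete data and common weeks the largest change in any estimate was 1.7e-14. Type I error falls only because the SE rises. With varying weeks and attrition together (62 triggered data sets, rho 0.5), the mean was -0.307 without and -0.308 with the covariate. Single data sets moved by 0.04 SD on average and by at most 0.13 SD.

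**Part (b): power at 34 per arm, 0.5 SD, two-sided 0.05 (noncentral t).** Variance per child is 1.974(1 - rho) for the slope, 1 - rho² for the baseline-adjusted last visit, and (1 + rho)/2 - rho² for the baseline-adjusted average of both later visits. At rho 0.5:

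- Slope: SE = √(2 × 0.987/34) = 0.241. A linear effect gives 0.5/0.241 = 2.08. An effect already full at post-intervention gives 0.526/0.241 = 2.18.
- Adjusted last visit: SE = √(2 × 0.75/34) = 0.210, ratio 2.38.
- Adjusted average: SE = √(2 × 0.5/34) = 0.171, ratio 2.92.

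| Analysis | rho 0.3 | rho 0.5 | rho 0.7 | rho for 80% |
|---|---|---|---|---|
| Planned slope, linear effect | 41% | 53% | 75% | 0.73 |
| Planned slope, sustained effect | 44% | 58% | 79% | 0.71 |
| Adjusted last visit | 57% | 65% | 81% | 0.69 |
| Adjusted average, sustained effect | 77.5% | 81.9% | 92.3% | 0.44 (within 0.3-0.7) |

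One-sided, 80% is reached at rho 0.57 for the adjusted last visit and at 0.66 or 0.62 for the slope. Using the baseline and post-intervention data of six further dyads per arm raises slope power to 44/57/78% (linear) or 50/63/84% (sustained). If the baseline-to-follow-up correlation is only 0.8 rho, slope power for a linear effect falls to 38/46/59% and adjusted last-visit power to 55/60/69%.

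**The case against.** The strongest reply is that the reach is small. The form of entry is unstated, so the defect depends on a reading. Each outcome triggers in about 5% of trials. Over all randomisations the slope is unbiased with about 5% type I error. The outcomes are secondary, the primary endpoints in 6.1 are feasibility and acceptability, and the planned baseline comparison would make an imbalance visible. All of this stands, and it limits the weight of the point. It does not rescue the rule, which acts only in imbalanced trials and on average does not correct there. Section 6.4 lists about 11 sleep and behavior outcomes (some may be categorical), so 11 × 0.05 = 0.55 triggers are expected per trial.

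A reader might infer that any triggered report carries exactly the full shift. That does not follow: visit weeks vary and dyads are lost, so a single estimate can move somewhat. The result is about the average.

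A reader might also infer that the trial is underpowered, or that 80% needs a high correlation under any analysis. The documents support neither. Section 6.5 names no visit and no sidedness, and a one-sided test or an average over both visits reaches 80% at moderate correlations. Part (b) is a mismatch between two sections.

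**Conclusion.** The point holds in two limited parts.

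(a) With main-effect entry and a continuous outcome, the triggered covariate leaves group by time unchanged: exactly so with complete data and common weeks, on average otherwise. About 0.74/0.53/0.32 of a chance imbalance stays at rho 0.3/0.5/0.7, and the covariate mainly enlarges the SE. The error is conditional on imbalance. Nothing is claimed for the logit models, which were not evaluated.

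(b) The power above 80% in 6.5 is for an analysis that 6.4 does not plan. For lack of stated inputs it can be neither confirmed nor refuted. Under the assumptions above, the planned slope has less power than the adjusted last visit at rho 0.3 and 0.5, and the gap narrows at 0.7.

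Both should be fixed, because 6.5 makes effect-size estimation the main goal. The sizes rest on assumed correlations, equal allocation and compound symmetry.

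**What to change.** Delete the significance-triggered rule. For every continuous outcome, adjust for its own pre-intervention value whether or not the arms differ, by one of two routes:

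- Post-intervention and follow-up values as responses, with group, visit (categorical), group by visit, baseline, and baseline by visit.
- A constrained-baseline model, which keeps dyads without post-baseline data. It was not simulated here.

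Name the covariance in advance, preferably unstructured. With a random intercept, 15% attrition and compound-symmetric data, the first route kept type I error at 4.2-5.6% in triggered trials, with a shift of at most 0.01 SD. When the baseline-to-follow-up correlation was only 0.8 rho (complete data), type I error at follow-up was 5.7/5.5/6.3%.

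Do not simply add baseline and baseline by time to a growth model that keeps baseline as a response. Its SEs are too large (0.248/0.222/0.181 against empirical SDs of 0.203/0.191/0.158), and type I error falls to about 2%.

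Report adjusted differences with 95% CIs at each visit and averaged; the linear slope may stay as supportive. State which outcomes are categorical and how baseline enters their models. Restate the 6.5 power for the chosen analysis with its correlation and source, alpha, sidedness and visit.

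Cost: one paragraph of 6.4 and the power sentence of 6.5, with no new data. The slope p-value becomes supportive, the restated power may fall below 80%, and under the first route dyads with no post-baseline data drop out.

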### Study Interventions and Measures:

[figure not shown]
Sleep Well! is a brief, behavioral sleep intervention for toddlers and preschoolers who have a caregiver-reported sleep problem or who are not getting enough sleep. The intervention includes evidence-based behavioral sleep approaches and strategies to engage and empower families. The primary study outcomes are the feasibility of recruitment, randomization, and measurement procedures; intervention acceptability; and intervention engagement and adherence. Secondary outcomes are the direction and magnitude of objective and caregiver-report child sleep and behavior at post-intervention and follow-up.

---

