### **3.4 Study Population**

#### **3.4.1 Inclusion Criteria**

- 1) Parental/guardian permission (informed consent)
- 2) Caregiver participant is the parent or legal guardian of the child subject
- 3) Caregiver/legal guardian  $\geq 18$  years of age.
- 4) Child between the ages of 1 and 5 years.
- 5) Presence of caregiver-reported child sleep problem determined by a Brief Child Sleep Questionnaire item included in an eligibility screening questionnaire (see below) or child meets American Academy of Sleep Medicine diagnostic criteria for either pediatric insomnia or insufficient sleep, assessed through an eligibility screening questionnaire.
- 6) English-speaking.

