### 5.3 Demographic and Parent and Child Behavior Measures (Secondary Outcomes and Covariates)

- *Child Demographic Information:* Child demographic information will be abstracted from the EMR (see section 5.1.1).
- *Caregiver Demographic and Family Questionnaire:* Caregivers will complete a caregiver and family demographic questionnaire at baseline. Child data will include CHOP primary care site where child receives care, whether the child attends daycare/preschool, and where the child typically sleeps. Caregiver/family data will include age, sex, race, ethnicity, highest educational level obtained, relationship to child, income, employment status, relationship status, number of times the family has moved in the last year, and information about children and adults living in the home.
- *Previous Service Use Form:* At each assessment, caregivers will complete a form related to any previous treatment for child sleep or behavior problems.
- *Brief Child Sleep Questionnaire (BCSQ):* Caregivers will complete the BCSQ to report on child sleep habits (sleep time, total sleep durations, night wakings, aspects

of the sleep environment, etc.) and the severity of any caregiver-perceived sleep problems. The BCSQ is appropriate for children ages 1-5 years and has shown good reliability and moderate correspondence with actigraphic recordings of child-sleep. There will be an attention check item placed randomly within the questionnaire, which is designed to detect individuals who are quickly responding to survey questions without sufficient attention to item content. Previous research has demonstrated that the inclusion of an attention check item can increase questionnaire reliability.

- *7-Day Daily Child Sleep Diary:* Items drawn from the BCSQ will be used to track regularity in child bedtime routines, bedtime activities, and 24-hour sleep schedule over 7 days at baseline (pre-intervention) and follow-up (post-intervention).

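### The BCSQ sleep-problem outcome is also an entry route, so its baseline is probably high; if it is coded yes/no, the group × time test in section 6.4 becomes imprecise

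*Combined protocol and SAP*

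**What the plan says.** Section 3.4.1, criterion 5, has two routes joined by an or. The first is "Presence of caregiver-reported child sleep problem determined by a Brief Child Sleep Questionnaire item". The second is meeting "diagnostic criteria for either pediatric insomnia or insufficient sleep, assessed through an eligibility screening questionnaire". The abstract describes the same two groups: "toddlers and preschoolers who have a caregiver-reported sleep problem or who are not getting enough sleep".

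The BCSQ is completed again at the baseline assessment, 0–3 weeks after screening (sections 3.1 and 4.2), and later at post-intervention and follow-up. Section 5.3 says that it records, among other things, "the severity of any caregiver-perceived sleep problems".

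Section 6.4 lists "Child sleep problems (BCSQ" first among the secondary sleep outcomes, without naming the item or its scale. On the model it says: "Categorical outcomes will be modeled as mixed-effects growth models with maximum likelihood and a logit link". On the terms: "Models will account for random effects (intercept, time) and fixed effects (group, and time by group". Time starts at the pre-intervention assessment, so the group term is the baseline difference between the arms. The test is the interaction: "The time by intervention group interaction identifies whether there is a significant between-group difference in change since pre-intervention". For categorical outcomes the reported effect size is the percent change in the odds from that same interaction.

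**The concern.** An outcome that also selects participants starts from a restricted baseline. If most children have the problem at time 0, the baseline log-odds in each arm rests on the few who do not. The planned model still estimates a separate baseline value for each arm, although randomisation makes the true difference zero. The uncertainty in that difference passes straight into the group × time slope. A real post-baseline difference can be partly absorbed by a chance group term at time 0.

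What is at stake is the test for this outcome and, more to the point, the effect size. Section 6.5 gives estimation of effect sizes for a later trial as the study's main goal. The plan does not discuss the baseline distribution of this outcome.

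**Working it through.** **1. The plan's own figures.** Section 6.5: 68 / (1 − 0.15) = 80, which agrees. The power of more than 80% is for a 0.5 SD effect on a continuous outcome by linear regression with covariates. With 34 per arm, two-sided 5% and no gain from covariates, power is Φ(0.5·√(34/2) − 1.96) = Φ(2.06 − 1.96) = 0.54. The stated figure therefore needs a covariate correlation of about 0.69, which is not given. That is a separate matter. No power is stated for any categorical outcome, so there is nothing to reproduce for this one.

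**2. Baseline prevalence.** Let q be the share positive on the item at screening, r the share of these still positive at baseline, and s the share positive at baseline among those who entered by the other route. Prevalence = q·r + (1 − q)·s. None of the three is in the documents. I assume r = 0.9–1 and s = 0–0.25.

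| q | Lowest | Highest |
|---|---|---|
| 1 | 0.9 = 90% | 100% |
| 0.9 | 0.9·0.9 = 81% | 0.9 + 0.1·0.25 = 92.5% |
| 0.8 | 0.8·0.9 = 72% | 0.8 + 0.2·0.25 = 85% |

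This gives about 72–100%. With q = 0.7 it would be 63–77.5%.

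**3. Mechanism in closed form.** Take 34 per arm, one follow-up visit at 75% vs 40% (assumed), and visits treated as independent. The log odds ratio is ln(0.75/0.25) − ln(0.40/0.60) = 1.50. SE² is the sum of 1/(n·p·(1 − p)) over the four arm-by-visit cells. The two follow-up cells add 1/(34·0.1875) + 1/(34·0.24) = 0.279. The two baseline cells add 2/(34·p·(1 − p)).

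| Baseline p | Baseline part | SE | Power | 95% CI factor on the odds ratio, exp(1.96·SE) |
|---|---|---|---|---|
| 50% | 0.235 | 0.72 | 0.55 | ×/÷ 4.1 |
| 80% | 0.368 | 0.80 | 0.46 | ×/÷ 4.8 |
| 90% | 0.654 | 0.97 | 0.34 | ×/÷ 6.6 |
| 95% | 1.238 | 1.23 | 0.23 | ×/÷ 11 |
| 99% | 5.942 | 2.49 | 0.09 | ×/÷ 130 |

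Only the baseline part changes.

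**4. Simulation of the planned model.** 80 dyads, 1:1, two-sided 5%, true rates 75% vs 50% at both later visits (all assumed except the 80). Three set-ups were run. Two have random intercept and slope, weeks 0/12/19, 15% missing at follow-up and latent correlation 0.5, with 200 runs each. One has a random intercept only, with 120 runs. The graded column is an assumed five-level item in an ordinal logit growth model.

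| Baseline | Planned test, yes/no | Planned test, five levels |
|---|---|---|
| near 100% | 2%, 11%, 12% | 72% |
| 95% | 18%, 27% | 84% |
| 90% | 27%, 35%, 40% | 85% |
| 80% | 44%, 52% | 87% |

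For the yes/no item, a comparison on the two post-baseline visits gives 80–85% and a common-baseline growth model 86–88%. For the five-level item a further run gives 71–88% for the planned test, 95–98% with a common baseline and 93% post-baseline. Simulation error is about √(0.4·0.6/200) = 3.5 percentage points. With no true effect the two alternatives reject in 2–8% of runs, within simulation noise of 5%.

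**5. Other effect sizes.** 34 per arm, weeks 0/12/20, latent correlation 0.4, random intercept only. At 75% vs 40%, planned power by baseline is 0.71 (50%), 0.67 (75%), 0.55 (85%), 0.46 (90%), 0.30 (95%) and 0.08 (100%). Follow-up alone gives 0.87 and a common baseline about 0.97. At 75% vs 57%, planned power falls from 0.29 (50%) to 0.12 (90%) and 0.06 (95%), against 0.37 and about 0.53. A five-level score analysed linearly keeps 0.81–0.92 for the larger effect and 0.38–0.47 for the smaller.

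**The case against.** A reader might infer that the screening item alone decides eligibility, so that baseline is near 100% in both arms by rule and the test must lose most of its power. The documents do not support that. The second route admits children who are negative on the item, the share entering that way is not given, and the BCSQ is asked afresh at baseline up to three weeks later. It is also an inference that the outcome is the screening item and that it is yes/no. Section 5.3 mentions severity, and the logit model in section 6.4 has threshold parameters, so it can take a graded item. With grades kept, most of the loss disappears. These points stand, and they make the finding conditional.

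Nor is the whole gap due to eligibility. With a 60% baseline and later rates of 50% vs 25% (the same odds ratio of 3), the planned test has 54% power against 78% for the post-baseline comparison. Measured against that 54%, the 40% found in the same set-up at a 90% baseline is a loss of about a quarter (14/54). The free baseline term costs power at any baseline; a high baseline makes it worse.

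Finally, this is one of several secondary outcomes in a pilot with descriptive primary endpoints, and the worked examples in section 6.5 are other sleep measures. That limits the consequence. It does not remove it, because the effect size for this outcome comes from the affected term.

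**Conclusion.** The concern holds in conditional form. Selection and outcome share a questionnaire and a construct, the baseline is likely to be high, and the plan leaves open the scale that decides whether its analysis works. Coded yes/no, the planned test loses most of its power only at baselines of about 95% or more; at 80–90% the loss is partial but still material beside the alternatives. Coded as a severity grade, the loss is modest. Both alternatives beat the planned test for every coding and baseline compared.

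The sizes rest on assumed event rates, correlations, 1:1 allocation, a two-sided 5% level and, for the graded case, five levels with assumed cut-points. The ordering of the methods is firmer than any single figure. The change is worth making because it costs almost nothing, not because the trial's main conclusions depend on it.

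**What to change.** In section 6.4:

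- Name the BCSQ item behind the sleep-problem outcome, say whether it is the screening item, and give its response scale. Analyse it on the graded severity scale where the item allows.
- Either constrain the arms to a common baseline (drop the group main effect at time 0 and keep time and group × time), or compare the arms on the post-intervention and follow-up answers, linked by child, with baseline severity as a covariate.
- State that criterion 5 restricts the baseline value of this outcome but does not fix it, and report the observed baseline distribution by arm.
- State that the baseline BCSQ is answered before the family learns its allocation, since the common-baseline constraint relies on this. Section 4.2 lists the questionnaires ahead of randomisation, while section 3.1 lists random assignment ahead of the baseline measures.

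Cost: a few lines of wording and no new data. This outcome is modelled and reported slightly differently from the others.
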